6.0 Provisions to Monitor the Data to Ensure the Safety of Subjects

Data and Safety Monitoring Plan

The purpose of the data and safety monitoring plan is to establish standards that will ensure that this protocol complies with Federal Regulations, Health Insurance Portability and Accountability Act (HIPAA) requirements, and applicable Dana-Farber Harvard Cancer Center (DF/HCC) Standard Operating Procedures.

General Approach: We have developed a comprehensive data and safety monitoring plan for the proposed project. Throughout the award period, weekly meetings will take place with the research team: [name] and [name], MPH, and study staff. Specifically, meetings will include ongoing review of study protocol, assessment procedures, and issues

related to recruitment, data collection, and management. Study staff will also discuss any human subject issues that arise.

General Roles and Responsibilities: We will use several coordinated strategies to monitor study recruitment, enrollment, and retention, as described in the following table. We will also closely track collection of patient-reported assessments, as these measures are an essential aspect of our study procedures and outcomes. For all strategies identified in the table, we will develop study tracking forms that will be reviewed at the weekly team meetings. Study tracking forms will be used to create a record of all decisions made and actions taken. I will send a report ahead of the meeting detailing study progress and setting the agenda. The following monitoring and reporting steps will be taken for each study activity:

Study Activity	Monitoring and Reporting Mechanism
Recruitment	
 • The designated CRC will generate a weekly report outlining the number of patients approached and reasons for ineligibility or disinterest in study participation.
Informed Consent	
 • The CRC will generate a weekly report detailing the number of participants who consented to the study. • The PI will go through any issues related to informed consent with the CRC weekly or earlier if urgent.
Enrollment	
 • The CRC will generate a weekly enrollment report.
Assessments	
 • The CRC will conduct a review for completeness and accurate data entry. • The CRC will maintain participant records of distress levels at each timepoint and follow Reaction Management if required.
Intervention	
 • The CRC will contact patients to test the videoconferencing technology. • The PI and trained study staff will review at least 10% of audio-recorded treatment sessions. • The CRC will maintain a record of participant progress in sessions, including attendance.
Retention	
 • The CRC will generate a weekly report detailing completion of follow-up assessments and retention strategies implemented for each participant. • The CRC will generate a weekly report of all participants who withdraw from study.
Analysis	
 • The PI will work closely with study biostatistician, [name] (scientific advisor in biostatistics), on all qualitative and quantitative analyses.

Specific PI Roles and Responsibilities

I will be responsible for all aspects of conducting the protocol; I will:

- Oversee the coordination, development, submission, and approval of the protocol to the DF/HCC as well as subsequent amendments.
- Ensure that the investigators and study staff are qualified and appropriately resourced to conduct the protocol.
- Carry out a Data and Safety Monitoring Plan as detailed in this document.
- Ensure that each participating study staff member receives adequate protocol training prior to enrolling participants and throughout the trial's conduct as needed.
- Monitor progress and overall conduct of the study.
- Conduct review of 10% of intervention sessions for process and content fidelity.
- Conduct weekly supervision for clinical protocol interventionists.
- Review data and maintain timely submission of data for study analysis.

- Ensure compliance with all requirements as set forth in the Code of Federal Regulations, DF/HCC, HIPAA requirements, and the approved protocol.
- Commit to provisions that the protocol will not be rewritten or modified by anyone other than the overall PI.
- Monitor accrual and address concerns if accrual goals are not met.

The Massachusetts General Hospital Cancer Center is expected to comply with all applicable federal regulations and requirements, the protocol and HIPAA requirements. Specifically, it will:

- Oversee the data collection process.
- Maintain documentation of Serious Adverse Events (SAE) reports and deviations/violations.
- Maintain regulatory documents which include but are not limited to the following: IRB approvals/notifications, confirmation of Federal wide Assurances (FWAs), all SAE submissions, screening logs, and IRB approved consents.
- Conduct regular communications with the PI and maintain documentation of relevant communications.
- Document the delegation of research specific activities to study personnel.
- Maintain regulatory files.
- Have office space, office equipment, and internet access that meet HIPAA standards.
- Participate in quality assurance activities and meet with monitors or auditors at the conclusion of a visit to review findings.
- Promptly provide follow-up and/or corrective action plans for any monitoring queries or audit findings.

Informed Consent Requirements. The DF/HCC approved informed consent document will serve as a template for the informed consent.

Protocol Confidentiality. All documents, investigative reports, or information relating to the participants are strictly confidential. Confidentiality is assured as participants will be identified on all study materials only by participant number, visit number, and date of visit. By recording the study data in this manner, the information can be considered 'de-identified,' and therefore compliant with the Standards for Privacy of Individually Identifiable Health Information ("Privacy Rule") of HIPAA. Participants' data will be kept in a computer file that is password protected and this password will be changed whenever the staff changes. This password-protected file will be stored on the encrypted MGH network drive on hospital computers. Only the Principal Investigator and study staff will have access to the data. We will keep a link between participant number and participant's name in a separate file, also password protected (with a different password).

Data Management Organizational Structure Data. Study forms will undergo a systematic and rigorous editing process prior to being keyed into the database. The research assistant will routinely evaluate the data and discuss any problems and questions with the study staff, myself, and mentors at the regular weekly team meetings. Data management formal reports on record status across the three following domains will be employed: entered, verified, and edited. These reports of data records will be evaluated once a month during the final team meeting of the month. All study data (including data from the Electronic Health Record) will be stored on the encrypted MGH network drive on hospital computers and will be password protected. To ensure data protection, backup copies automatically generated by MGH computer systems will be available.

Data Safety and Monitoring Plan. The following procedures will be followed, in compliance with NIH requirements, to ensure the safety of study participants and the validity and integrity of data:

Data Repository: The MGH Cancer Outcomes Research Program (CORE) has coordinated research initiatives over the past ten years that have established procedures and technologies for data collection and management. I will oversee all aspects of data collection for the study and the research assistant will have the operational responsibility of data management. We will develop a study specific data management protocol and standard operating procedures for the creation and testing of all study forms, data collection, quality control, and data extraction. These forms will be standardized. We will provide ongoing oversight of data management

throughout the study, and will be responsible for generating reports and datasets for quality control and data analysis. All data management activities will utilize REDCap, a HIPAA-secure, web-based survey application for electronic collection and management of research and clinical trial data. REDCap data collection projects rely on a thorough study-specific data dictionary defined in an iterative self-documenting process by all members of the study staff with planning assistance from Partners HealthCare Research Computing, Enterprise Research Infrastructure & Services (ERIS) group. REDCap provides an intuitive interface for users to enter data and have real time validation rules (with automated data type and range checks) at the time of entry. Data management reports will be generated weekly and discussed during the study staff meetings.

- **Serious Adverse Events:** Expedited review will occur for all events meeting the Food and Drug Administration (FDA) definition of a SAE (i.e., any fatal event, immediately life-threatening event, permanently or substantially disabling event, event requiring or prolonging inpatient hospitalization, Unanticipated Problems [UPs], or any congenital anomaly). This also includes any event that a study investigator judges to impose a significant hazard, contraindication, side effect, or precaution. For purposes of this study, all SAEs will be required to be reported to the PI, the DF/HCC IRB, and federal agencies (National Cancer Institute, FDA, and the NIH Office of Biotechnology Activities), regardless of any judgment of their relatedness to the study. All relevant information will be reported to the study investigators for each SAE including information about the event and its outcome, study condition, concomitant medications, the subject's medical history and current conditions, and all relevant laboratory data. Notification by secure e-mail of all related study forms shall be made to the DF/HCC IRB within 24 hours of the occurrence of any SAE. Information will be reviewed and a determination made of whether there was any possible relevance to the study interventions. Reporting to NIH will be made according to their respective regulations governing SAE reporting.
- **Non-Serious Adverse Events:** At weekly meetings, the study staff will discuss summaries of the numbers and rates of adverse events by treatment group. These reports will include types of events, severity, and treatment phase.
- **Other Safety-Related Reports:** At weekly meetings, the study staff will discuss summary reports of treatment retention and reasons for dropout or withdrawal by treatment group.
- **Study Stopping Rules:** We do not have a pre-specified stopping rule given the low-risk nature of the proposed study. However, if at any point the DF/HCC or the study investigators judge that the risks of study procedures outweighs the benefits, the project will be stopped immediately.
- **Procedures to ensure confidentiality, preparation of reports, minutes, and recommendations:** We will work with the CRC to prepare study reports and circulate them to the study staff during the weekly scheduled project meetings. These reports will include overall study progress and safety data. At the conclusion of each research group meeting, the investigators will determine whether any changes in the conduct of the trial are recommended.

7.0 Statistical Analyses

7.1 Primary and Secondary Endpoints

Our primary endpoint of this phase of feasibility and acceptability will be measured by rates of enrollment (>50%), participant retention (70%), intervention attendance (>70% attending at least 1 of 2 sessions), and intervention satisfaction (>75% reporting satisfaction greater than the CSQ's midpoint).

Our secondary aim is to assess intervention-related changes in primary and secondary outcomes at one- and three- months post-baseline. We will explore changes in satisfaction with patient-physician communication, perceived social support, self-efficacy for symptom management, and quality of life.

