AET initiation is a modifiable health behavior with established predictors, with some being more salient for minority BCS. Adherence to guideline concordant care is the single most modifiable factor that influences treatment outcomes for BCS.¹² Modifiable factors associated with non-initiation of AET include (1) low perceived social support and poor communication with clinicians, (2) negative beliefs about treatment efficacy, and (3) fears of toxicities. First, BCS who report a lower quality of communication with their physicians, less social support and greater difficulty making decisions around AET treatment are less likely to initiate.^{3,13} Notably, quality of communication about AET and clinician trust is rated lower among Black BCS than Whites.¹⁴ Among low-income Latina women, patient-centered communication may increase AET use.¹⁵ Second, non-initiators are more likely to hold negative beliefs about therapeutic efficacy and less favorable attitudes towards AET.³ Across all racial and ethnic groups, discontinuation is associated with questions about “whether AET is helping.”¹⁶ Third, adverse effects (e.g., joint pain, hot flashes, sleep difficulties) are common with AET and patients who express greater fears about these side effects are less likely to initiate.³ While fears of side effects are present across all racial/ethnic groups, one study suggested that side effects were the most cited barrier to AET use among Hispanic patients.⁹ In addition, BCS who report receiving inadequate information about managing side effects are less likely to initiate.¹⁶ Ultimately, poor clinician-patient

communication and social support, doubts about efficacy, and fears of side effects are modifiable contributors to AET initiation, and certain barriers are more pronounced in racial and ethnic minorities.

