1.4 Innovation of Proposed Study

This research project aims to reduce risk of recurrence and prevent second primary breast cancer by increasing initiation of AET for BCS who have failed or delayed AET initiation or are hesitant to start, with particular

attention to Black, Hispanic/Latina and Asian American BCS. The data from this Phase 2 single-arm pilot trial to test a behavioral intervention developed using feedback from Phase 1 (21-331) to improve initiation, will be used to apply for an NIH grant to conduct a full-scale efficacy trial of the intervention. This is an area of important clinical investigation that does not necessitate a new treatment or technology, but rather points to the critical need to improve how and whether patients engage with an efficacious, life-saving therapy. In the short-term, this study has the potential to improve understanding of AET need and efficacy and increase initiation by mitigating barriers and enhancing self-efficacy. To minimize burden and increase access, we propose to deliver the intervention via ZOOM™, a HIPAA-secure Massachusetts General Hospital (MGH)-approved software. The study staff may also administer these sessions in person or via phone if necessary. This intervention has minimal risk and is likely to improve patient satisfaction with communication with clinicians and management of AET-related side effects. In the long-term, this study may improve patient outcomes by preventing second primary tumors, recurrence, and disease-related mortality while promoting the quality of life of BCS and reducing the racial and ethnic disparity in breast cancer outcomes.

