5.0 Study Design and Methods

5.1 Design/Study Type

The present protocol proposes to examine the single-arm pilot trial to examine feasibility and acceptability of a patient-centered, evidence-based, culturally competent, tailored intervention to encourage breast cancer survivors who have not begun taking adjuvant endocrine therapy to initiate the medication, enriching for Black, Hispanic/Latina, and Asian American BCS. AET initiation will be measured by a self-report questionnaire. Participants will complete assessments at baseline (within 14 days of consent), 1-month, and 3-months post-baseline measuring beliefs about AET necessity, satisfaction with patient-physician communication, perceived social support and quality of life.

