7.2 Sample Size

To determine feasibility in a single-arm pilot trial (up to N=35), estimate effect size, and finalize the intervention and study protocol to apply for an NIH grant to conduct a full-scale efficacy trial.

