7.5 Analysis Plan

Aim 1: Feasibility and acceptability will be measured by rates of enrollment (>50%), participant retention (>70%), intervention attendance (>70% attending at least 1 of 2 sessions), and intervention satisfaction (>75% reporting average satisfaction greater than the CSQ's midpoint).

Aim 2: First, data will be analyzed with the intention-to-treat principle and assessed for statistical assumptions and patterns of missingness, implementing Multiple Imputation with maximum likelihood if appropriate. Sample size justification. We may over-accrue to ensure that a total of up to 45 BCS complete the study. This pilot study will provide a preliminary estimate of the rate of AET initiation within one month from baseline. With up to 30 participants, the width of the exact 95% confidence interval (CI) for the rate of AET initiation at one month will be at most 37.4% (i.e., +/- 18.7%). If at least 24% of participants initiate AET within one month, the study will rule out a post-intervention initiation rate of lower than 10% based on the lower limit of the exact 95% CI. We will conduct exploratory analyses to examine whether participants' baseline characteristics are associated with AET initiation at one month using Fisher's exact tests and unpaired t-tests. For secondary outcomes, we will conduct paired samples t-tests to assess intervention-related changes in satisfaction with communication with clinicians and treatment, Necessity-Concerns Framework, perceived support, self-efficacy for managing side effects, and QOL from baseline to one-month post-baseline. In addition, we will use linear mixed effects regression models to evaluate the change in secondary outcomes across all three assessment time points. We will interpret 95% Confidence Intervals and Cohen's d effect sizes ($D = [(Mean 1) - (Mean 2)] / \text{pooled Standard Deviation}$), with magnitudes of 0.3, 0.5, and 0.8 for small, medium, and large effects, respectively. We will conduct sensitivity analyses to examine whether changes in outcomes are differ among racial and ethnic groups.

Participants will be given the opportunity to receive a summary of study results at the completion of the study. If a request is made, the study staff will provide the participant with an abstract of the study at the end of data collection and analysis.

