7.6 Handling of Missing Data in the Analysis

The analyses for this study will focus on study completers to estimate the effect of the 2-session, patient centered intervention. The primary endpoint will be based on acceptability and feasibility aspects of the study. We will use the intention-to-treat principle for analyses with all participants. After we examine patterns of missingness, we will use maximum likelihood with multiple imputation to account for missing data.

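### Within-group changes in a single-arm pilot are called intervention-related and read as an effect, which the design can describe but not attribute

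*Combined protocol and SAP*

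**What the plan says.** Section 5.1 describes the design: "The present protocol proposes to examine the single-arm pilot trial to examine feasibility and acceptability". No section names a control group, an external comparison or a lead-in period.

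Four places nevertheless use the language of attribution:

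- **Sections 2.0 (Aim 2) and 7.1** aim to "assess intervention-related changes in primary and secondary outcomes" at one and three months.
- **Section 7.5** gives the method for the secondary outcomes: "we will conduct paired samples t-tests to assess intervention-related changes in satisfaction with communication with clinicians and treatment", and for the other secondary scales, from baseline to one month. It adds linear mixed models over the three assessments, and Cohen's d read against benchmarks of 0.3, 0.5 and 0.8.
- **Section 7.6** says the focus on completers is there to "estimate the effect of the 2-session, patient centered intervention".
- **Section 7.2** gives the purpose of the sample: "To determine feasibility in a single-arm pilot trial (up to N=35), estimate effect size, and finalize the intervention and study protocol". The same sentence goes on to the grant application for a full-scale efficacy trial. Section 1.4 says the pilot data "will be used to apply for an NIH grant to conduct a full-scale efficacy trial of the intervention".

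No section cautions that change from baseline may have other causes.

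**The concern.** A paired t-test, a mixed model with time as the predictor, and d computed from two time points in one arm all target the same quantity: the average change from baseline in these women. That is the effect of the intervention only if nothing else would have moved the scores. The protocol itself describes several things that could.

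Two consequences are possible. A significant paired test could be reported as a result of the intervention when it reflects the passage of time. And a within-group d could be mistaken for the between-group difference an efficacy trial should be designed to detect, since Section 7.2 mentions effect size and the efficacy-trial application in one sentence and does not limit its use.

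**Working it through.** **1. The plan's own figure.** Section 7.5 states that, with 30 participants, the exact 95% CI for the one-month initiation rate is at most 37.4% wide. The Clopper-Pearson interval is widest at 15/30, running from 31.3% to 68.7%, a width of 37.4%. The figure reproduces. The companion statement, that at least 24% initiating rules out a rate below 10%, also holds: 24% of 30 is 7.2, so at least 8/30 is needed, and the lower limit at 8/30 is 12.3%. Both statements concern the precision of one proportion. Neither compares it with what would happen without the intervention, and the documents do not say that 10% is the untreated rate. So the fault is one of interpretation, not of arithmetic.

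**2. What the one-arm analysis estimates.**

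Observed change = intervention effect + background change.

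One arm yields only the sum. The documents point to these sources of the second term:

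- *Starts that would have happened anyway.* Nobody is taking endocrine therapy at screening (Section 5.2), so the initiation rate can only rise. Some women have a recommended start still to come (Table 1), and the sessions are aimed to precede the agreed start date (Section 5.3). Starts as planned therefore follow the sessions by design.
- *Symptoms after those starts.* Section 1.2 says "adverse effects (e.g., joint pain, hot flashes, sleep difficulties) are common with AET", which could lower quality of life or confidence in managing symptoms.
- *Recovery after primary treatment.* Section 4.1 gives completion of radiation as an example of what precedes a future start, so follow-up can overlap recovery.
- *Usual care.* Section 1.2 says most oncology clinicians schedule a visit 3 to 4 months after prescribing to ask about initiation. It can fall within follow-up.

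Some of these would raise scores and some would lower them, so the net direction is unknown.

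**3. How often background change alone would be significant.** Inputs: n = 30 (Section 7.5). Background change g in SD units and pre-post correlation r are assumptions, because the documents give neither. With d_z = g / √(2(1 − r)) and noncentrality d_z√n, for a two-sided 5% paired t-test on 29 df:

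| g (SD) | r | d_z | noncentrality | chance of significance with no intervention effect |
|---|---|---|---|---|
| 0.2 | 0.5 | 0.20 | 1.10 | 19% |
| 0.3 | 0.5 | 0.30 | 1.64 | 36% |
| 0.2 | 0.7 | 0.26 | 1.41 | 28% |
| 0.3 | 0.7 | 0.39 | 2.12 | 54% |

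Under the present wording, each such result would be reported as intervention-related.

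**4. What would follow if a within-group d set the next trial's target.** Assume a 1:1 trial, two-sample t-test, two-sided 5%, 80% power, and an observed d of 0.5. That gives 64 per arm. At 64 per arm the noncentrality is δ√(64/2) = 5.66δ, where δ is what remains after background change is removed:

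| background part of 0.5 | δ | power at 64 per arm | n per arm for 80% |
|---|---|---|---|
| 0.1 | 0.4 | 61% | 100 |
| 0.2 | 0.3 | 39% | 176 |
| 0.3 | 0.2 | 20% | 394 |

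The table shows inflation only. If background change were negative, d would understate the effect and the error would run the other way.

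**The case against.** The case for leaving the text alone is that this is a pilot. Its primary endpoint is feasibility and acceptability. Sections 2.0 and 7.1 say several changes will be explored, and Section 7.5 speaks of a preliminary estimate of the initiation rate and plans to interpret confidence intervals alongside d. All of that stands and limits the weight of the point. It does not remove it: the labels in Sections 2.0, 7.1, 7.5 and 7.6 still attribute the change to the intervention, and no caveat is given.

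A reader might infer more than the documents support:

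- **That the pre-post d will size the efficacy trial.** No section says so. Section 7.2 puts effect size next to the application and Section 7.5 supplies d, but the step between them is an inference. The sample-size table above is therefore conditional.
- **That regression to the mean can be quantified from the hesitancy cut-off of 4.** The usual expression, shift × (1 − r), applies when people are selected on the outcome itself and the shift is measured from the population mean. Here selection is on a separate screening item, which Table 1 applies only to women with a future start. (The phone script in Appendix 9.5 applies it to everyone, but it is still not a follow-up outcome.) Any carry-over to the questionnaires depends on correlations the documents do not give.
- **That all side effects after starting are bias.** If the intervention leads a woman to start and symptoms follow, that is a downstream effect, and a randomised trial would count it too. Only starts that would have happened regardless belong to background change.
- **That a control arm is needed.** It is not, provided the claim matches the design.

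**Conclusion.** The point holds as one of interpretation. The plan describes total change from baseline as intervention-related and as an effect of the intervention, and a single arm cannot separate the two. This follows from the design and needs no assumption.

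Its size cannot be derived from the documents. Under assumed background change of 0.2 to 0.3 SD and correlations of 0.5 to 0.7, a pilot of 30 with no intervention effect would show a significant paired change 19% to 54% of the time. If 0.2 of an observed d of 0.5 were background, a trial of 64 per arm would have about 39% power for the remaining 0.3 and would need about 176 per arm. That second figure applies only if d is used to set the target difference, which the documents do not state.

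The correction is worth making because it changes what the secondary results can be said to show. The feasibility and acceptability endpoints are untouched.

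**What to change.** - **Sections 2.0, 7.1, 7.5 and 7.6:** replace the wording about intervention-related changes and about estimating the intervention's effect with *change from baseline*.
- **Sections 7.2 and 7.5:** report d only as a within-group change with its 95% CI, and state that it will not by itself set the target difference of the efficacy trial. State instead that the pilot will estimate SDs, pre-post correlations, retention and the initiation rate.
- **Optional:** tabulate change in FACT-B, HADS and self-efficacy by whether endocrine therapy was being taken at that assessment. The status question is already asked each time (Section 5.2). Label the table descriptive: status is itself a post-baseline outcome, so the split cannot separate intervention effect from background change. At the plan's 24% threshold it would rest on 7 or 8 starters out of 30 (0.24 × 30 = 7.2).

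The cost is a few sentences and a more modest secondary claim. No new data, visits or participants are needed, and no design figure changes.
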